5.6 Surgery

Participants who end the window period will proceed to standard of care total hysterectomy, with or without bilateral salpingo-oophorectomy. Route of surgery (e.g. open versus robotic laparoscopic versus laparoscopic versus vaginal hysterectomy) will be up to the discretion of the treating surgeon. Staging procedures (pelvic and/or para-aortic lymphadenectomies and/or omentectomy) will be at the discretion of the treating surgeon. Note: The procedure can be performed at an institution outside of COH, and tissue will be collected as per standard of care. Blocks or slides of the endometrial tumor from the hysterectomy specimen will then be requested following surgery by the research team.

Post-surgery, participants will enter follow-up (**Section 5.7**).

Assessment time points and windows are detailed in **Section 9.0**.

5.7 Follow-Up

All participants will enter post-surgery follow-up. This is comprised of post-surgery visit at: 6 weeks (\pm 14 days).

Note: Any reportable adverse events (AEs) occurring during follow-up should be followed until stabilization or resolution for all reportable AEs (per the agreement of the Study PI).

Assessment time points and windows are detailed in **Section 9.0**.

5.8 Duration of Study Participation

Study participation may conclude when any of the following occur:

Completion of study activities (treatment, pre-surgery activities and follow-up).

Withdrawal of consent (See **Section 16.5**).

Participant is lost to follow-up. All attempts to contact the participant must be documented.

At the discretion of the investigator for safety, behavioral, study termination or administrative reasons.

Documentation of the reason for discontinuing study participation and the date effective should be made in the medical record and appropriate eCRF. The COH DCC should be promptly notified of the change in participant status.

5.9 Supportive Care, Prohibited and Concomitant Therapies/Medications

Participants must be instructed not to take any additional medications (including over-the-counter products) during the trial without prior consultation with the investigator.

If concomitant therapy must be added or changed, including over-the-counter medications or alternative therapies, the reason and name of the agent/therapy should be recorded in the eCRF and documented in the EHR.

5.9.1 Prohibited therapies

The following medications are **prohibited** during the 30-day preoperative window period.

Other investigational therapy.

Other anti-cancer therapy.

5.9.2 Supportive care

With the exception of prohibited therapies (see **Section 5.9**), participants should receive prophylactic or supportive care as clinically indicated per institutional policies.

6.0 ANTICIPATED TOXICITIES

6.1 Pterostilbene

The following expected AEs are based on n=60 treated with PTE [23]. Asterisk (*) denotes $\geq 10\%$ and no asterisk denotes 1-10%:

Metabolism and Nutrition	Increased appetite
Musculoskeletal and Connective Tissue	Muscle pain

6.2 Megestrol Acetate

Per the 2017 package insert the expected toxicities for megestrol acetate are as follows (* signifies $> 10\%$; no asterisk signifies 1-10% and † signifies $< 1\%$):

Cardiac	Heart failure
Gastrointestinal	Nausea, vomiting
General Disorders and Administration Site	Malaise, asthenia, lethargy, sweating
Investigations	Increased weight*, high blood glucose
Metabolism and Nutrition	Glucose intolerance

Neoplasms benign, Malignant and unspecified (incl cysts and polyps)	Tumor flare reaction
Nervous system	Carpal tunnel syndrome
Psychiatric	Mood changes
Reproductive system and Breast disorders	Breakthrough menstrual bleeding, hot flashes
Respiratory, Thoracic and Mediastinal	Dyspnea
Skin and Subcutaneous Tissue	Alopecia, rash
Vascular	Hypertension, thromboembolic events, fatal thromboembolic events†

7.0 AGENT INFORMATION

7.1 Pterostilbene

[figure not shown]
Pterostilbene is not FDA approved for any indication.

7.1.1 Other names

3',5'-dimethoxy-4E-stilbenol, 3',5'-dimethoxy-resveratrol

7.1.2 Description and molecular weight

Pterostilbene is a naturally occurring analogue of resveratrol. It is found in several types of blueberries and unripe Pinor noir grapes.

Structural formula:	
Empirical formula:	C ₁₆ H ₁₆ O ₃
Molecular weight:	256.301
Chemical Name:	4-[(E)-2-(3,5-Dimethoxyphenyl)ethenyl]phenol

7.1.3 Mechanism of action

Preliminary studies suggest PTE has anti-tumor activities [25, 26].

7.1.4 Human toxicity

See **Section 6.1** for details.

7.1.5 Formulation

Oral capsule formulation supplement will be used for this trial.

7.1.6 Storage, handling

Follow package instructions.

7.1.7 Dose and administration

See **Section 5.3**.

7.1.8 Supplier

Pterostilbene is commercially available and will be purchased from Elysium Health.

7.2 **Megestrol Acetate**

Please refer to the package insert for a detailed description. Megestrol acetate has been FDA approved for indicated for the palliative treatment of advanced carcinoma of the breast or endometrium (i.e., recurrent, inoperable, or metastatic disease).

7.2.1 Other names

Megace

7.2.2 Description and molecular weight

Structural formula:	
Empirical formula:	C ₂₄ H ₃₂ O ₄
Molecular weight:	384.51
Chemical Name:	17 alpha-acethoxy-6-methylpregna-4,6-diene-3,20-dione

7.2.3 Mechanism of action

The precise mechanism by which MA produces its anti-tumor effects against endometrial carcinoma is unknown at the present time. Possible mechanisms may be via inhibition of pituitary gonadotrophin production and via local tumor effect.

7.2.4 Human toxicity

See **Section 6.2** for details.

7.2.5 Pharmacokinetics

Absorption:	Tablet- Time to peak concentration, 1 h to 3 h (mean 2.2 h)
Half-life elimination	13 h to 104.9 h (mean 34.2 h)
Metabolism:	Hepatic (to free steroids and glucuronide conjugates)
Excretion:	Urine (57% to 78%; 5% to 8% as metabolites); feces (8% to 30%) within 10 days

7.2.6 Formulation

Tablet formulation will be used for this trial.

7.2.7 Storage

Per package insert.

7.2.8 Dose and administration

See **Section 5.3**.

7.2.9 Supplier

Megestrol acetate is commercially available.

8.0 CORRELATIVE/ SPECIAL STUDIES

8.1 Correlative Tumor Tissue

An overview of collection, processing, and analysis details are shown below.

Table 1: Tumor Tissue Studies Overview

Tissue requirements	Timepoints of Collection	Receiving Lab	Downstream Analysis
Endometrial tumor obtained via endometrial pipelle (biopsy) or as endometrial curettings.	
Baseline (prior to therapy)Day of surgery	Pathology department →COH Pathology Core	See Section 8.1.3 .

Baseline endometrial biopsy –An office endometrial biopsy will be performed at COH Duarte unless the block or slides from a previous endometrial biopsy or curettings is available, which confirms diagnosis of endometrial cancer. These slides/blocks may be obtained post-informed consent. FFPE block of tissue or slides may be obtained at COH or outside institution

Day of surgery- an endometrial biopsy will be performed in the operating room while under anesthesia immediately before the hysterectomy if feasible. Alternatively, if the surgery is performed at a hospital other than COH, then the blocks or slides from the endometrial tumor from the hysterectomy will be requested and received by COH postoperatively.

8.1.1 Collection details

1. Prior to therapy initiation and following consent, the patient will undergo an office endometrial biopsy (see procedure description below) unless the block or slides from prior endometrial biopsy or curettings is available.
2. On day of surgery, following adequate anesthesia, perform endometrial sampling with an endometrial pipelle (see procedure description below), if feasible.

Endometrial biopsy procedure (optional):

Under sterile conditions, a standard endometrial biopsy will be used, which is a flexible polypropylene suction cannula with an outer diameter of approximately 3.1 mm.

- Introduce the pipelle into the intrauterine cavity.
- Perform three successive passes.

8.1.2 Labeling of samples if collected outside of Standard of Care

For collection at COH, samples will be labeled with the protocol ID, subject ID, date and time point of collection (per **Table 1**). If surgery is performed outside of COH, standard of care pathological collection will occur, and blocks or slides will be requested post-operatively by the research team.

8.1.3 Immunohistochemistry and pathology details

We will evaluate the correlation between expression of ER and PR in baseline specimen and hysterectomy specimens. ER and PR expression will be quantified by IHC based on intensity of staining (0 to 3+) and percentage of cells staining (0 to 100%). A modified H score will be calculated as the product of intensity X percentage of cells staining. We will examine the effects of PTE and MA on selected histologic and immunohistochemical measures of growth and apoptosis, including gland cellularity, nuclear grade, nucleoli, metaplasia, secretion, Ki-67, Bcl-2, and Casp3, to evaluate the mechanism of action of PTE and MA. These histologic and immunohistochemical measures were selected based on previously published results. [20, 24]. Exploratory endpoints include PTEN expression, presence of PI3K mutation, β -catenin mutation, MMR deficiency, and cyclin D1 correlation with histologic response. We will test the correlation between prognostic factors for endometrial cancer that are measured at baseline with histologic response. PTEN expression and MMR deficiency will be assessed by IHC as positive or negative. Presence of PI3K mutation and β -catenin mutations will be assessed by PCR as present or absent.

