10.0 ENDPOINT DEFINITIONS

10.1 Primary Endpoints

The **primary endpoint** is the tumor Ki-67 proliferation index, measured pre- and post-treatment in each treatment arm.

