10.2 Exploratory Endpoints

The **exploratory endpoints** are:

1. Measurements of histologic response, tumor growth, and apoptosis measured pre- and post-treatment in each treatment arm including:
 - o Response: gland cellularity, nuclear grade, nucleoli, metaplasia, eosinophilic cytoplasm, secretion
 - o Growth: Bcl-2
 - o Apoptosis: Casp3
2. Biological characteristics of tumors measured pre- and post-treatment in each treatment arm including:
 - o ER status
 - o PR status
 - o MMR status
 - o PI3K mutational status
3. Genomic analyses
 - o Germline and somatic genomic landscapes of endometrial tumor pre- and post-treatment in each arm
 - o Gene expression phenotypes before and after treatment:
 - driver mutations
 - mutation signatures
 - tumor mutation burden
 - immune signatures

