11.0 STATISTICAL CONSIDERATIONS

11.1 Study Design

This is an open-label randomized Phase II study to compare the efficacy of neoadjuvant MA plus PTE versus MA alone among EC patients undergoing scheduled total hysterectomy. The primary measure of efficacy will be treatment-associated change in tumor Ki-67 proliferation index. The primary endpoint of the proposed trial was chosen based on data from GOG-211 [24], where a 34.8% reduction in Ki-67 was reported following two weeks of MPA treatment.

11.2 The planned sample size is 18 evaluable participants per treatment arm. With 18 evaluable subjects per arm and using a 1-sided t test at $p<0.05$, the trial will provide 90% power to detect a difference in efficacy, favoring MA plus PTE, of at least 10% (with standard deviation 10%) in the mean reduction in Ki67. For example, the trial will be able to differentiate between a 40% and a 30% mean reduction in Ki67 per arm. Thus, the trial will study $2 \times 18 = 36$ evaluable subjects. Little dropout is anticipated due to tolerability issues or inconvenient protocol. Randomized allocation will be 1:1, allocated within strata of diagnosis and menopausal status.

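### The ER/PR score in Section 8.1.3 does not say which intensity applies when staining is mixed, and a single whole grade can miss or exaggerate a partial loss

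*Combined protocol and SAP*

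**What the plan says.** Section 8.1.3 names two readings for ER and PR: a staining intensity on a scale from 0 to 3+, and the share of cells that stain, from 0 to 100%. It then combines them: "A modified H score will be calculated as the product of intensity X percentage of cells staining". The section asks for no percentage at each intensity level and no sum over levels, and it gives no rule for assigning the intensity when levels are mixed. No other section defines the score further.

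The use tied to this quantity is stated in the same section: "We will evaluate the correlation between expression of ER and PR in baseline specimen and hysterectomy specimens". Section 10.2 places ER status and PR status among the exploratory endpoints, under "Biological characteristics of tumors measured pre- and post-treatment in each treatment arm including". Section 1.2 seeks biomarkers that could select patients in future studies, and Section 2.7 names ER and PR status among the tumour characteristics that may correlate with histologic response.

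The primary endpoint is separate. Under Section 10.1 it "is the tumor Ki-67 proliferation index, measured pre- and post-treatment in each treatment arm".

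**The concern.** A product of one intensity and one percentage treats all stained cells as if they had the same grade. When they do not, the result depends on which grade is entered, and the plan leaves that open. Two readers who both follow Section 8.1.3 can score the same slide differently.

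The second problem is sensitivity to change. The score is meant to be compared before and after treatment. With a commonest-grade rule it stays flat while part of the tumour weakens, then drops by a full grade or more across the whole stained fraction once the commonest grade switches. With a strongest-grade rule it stays flat for as long as any cells remain at the top grade. A partial loss of receptor staining is a change that a pre/post comparison should be able to show.

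At stake is the quality of the exploratory ER/PR expression data, and their value as a candidate selection marker for later studies.

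**Working it through.** The documents report no figure that rests on the H score, so there is none to reproduce. The check compares the product with the intensity-weighted sum.

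**Inputs.** From Section 8.1.3: intensity grades 0, 1, 2, 3; percentage staining 0 to 100; score = intensity × percentage. The documents give no distribution of cells over the grades, so every staining pattern below is an assumption for illustration.

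**Formulas.** Let p1, p2, p3 be the percentages of tumour cells at 1+, 2+ and 3+, and T = p1 + p2 + p3.
- Weighted sum: H = 1×p1 + 2×p2 + 3×p3, range 0 to 300.
- Product: g × T, where g is the single intensity entered. Section 8.1.3 does not define g for mixed staining, so four readings were tried: commonest grade, strongest grade, mean grade of stained cells rounded to a whole number, and unrounded mean.

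**Step 1: the unrounded mean.** Here g = H/T, so g × T = H. The product equals the weighted sum for every pattern, and there is no error.

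**Step 2: worked patterns with 80% of cells stained.**

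| Pattern | Weighted sum | Commonest grade | Strongest grade | Rounded mean |
|---|---|---|---|---|
| 80% at 3+ | 3×80 = 240 | 240 | 240 | 240 |
| 45% at 3+, 35% at 1+ | 135 + 35 = 170 | 3×80 = 240 | 3×80 = 240 | 2×80 = 160 |
| 35% at 3+, 45% at 1+ | 105 + 45 = 150 | 1×80 = 80 | 3×80 = 240 | 2×80 = 160 |

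Taking the first row as baseline:
- Second row: the weighted sum falls by 70/240 = 29%. The commonest-grade and strongest-grade products show no change.
- Third row: the weighted sum falls by 90/240 = 38%. The commonest-grade product falls by 160/240 = 67%, and the strongest-grade product shows no change. The same slide can therefore score 80 or 240.

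**Step 3: where the switch happens.** Start from 100% at 3+ (score 300) and let part of the cells fall to 1+.
- 49% fallen: H = 3×51 + 49 = 202; commonest-grade product still 300.
- 51% fallen: H = 3×49 + 51 = 198; commonest-grade product 100.
- 90% fallen: H = 30 + 90 = 120; commonest-grade product 100, strongest-grade product still 300.

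**Step 4: bounds.** Over all patterns on a 1% grid, product minus weighted sum lies between −100 and +99 points for the commonest grade (ties resolved to the lower grade), between 0 and +198 for the strongest grade, and between −50 and +50 for the rounded mean.

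**Step 5: how often the error is large.** This depends on how mixed the staining is. Shares at 0, 1+, 2+ and 3+ were simulated from a symmetric Dirichlet distribution. Parameter 1 spreads tumours evenly over all mixes; smaller values make tumours more homogeneous. Results for the commonest-grade product against the weighted sum:

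| Dirichlet parameter | Median absolute error | Off by more than 50 points | Correlation |
|---|---|---|---|
| 1 | about 29 | 25% | 0.85 |
| 0.3 | about 13.5 | 12% | 0.94 |
| 0.1 | about 1 | 5% | 0.98 |

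The mean error of the commonest-grade rule is about zero in all three settings. With parameter 1, the rounded-mean rule has a median error of about 17 points, none above 50, and a correlation of 0.91.

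**The case against.** The strongest reply is that the plan calls the score modified and defines the modification openly, so it is a deliberate simplification of an exploratory marker and nothing in the documents contradicts it. That stands as far as it goes: this is an under-specified measurement rule, not an inconsistency. But the label does not tell the reader which intensity to enter for a mixed specimen.

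A reader might infer that the product is wrong for every tumour with mixed staining. The documents do not support that. The text never says that the intensity must be a single whole grade. An unrounded mean removes the error, and even a commonest-grade rule is exact for some mixes: with 20%, 40% and 20% at 1+, 2+ and 3+, the product is 2×80 = 160 and the weighted sum is 20 + 80 + 60 = 160.

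A reader might also take the worked patterns as typical. There is no basis for this, because the documents give no ER or PR intensity data. If most tumours stain homogeneously, the usual error is about a point.

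Finally, a reader might infer that all ER/PR analyses, or the power of the 36-patient trial, are compromised. Sections 2.7 and 10.2 refer to ER and PR status without invoking the H score, and no cut-point links the two. No effect on an arm comparison or on a trial decision has been shown.

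**Conclusion.** The point holds in a limited form. Section 8.1.3 leaves the intensity undefined for mixed staining. Under either single-grade reading, the product can hide a 29% fall in the weighted score, or turn a 38% fall into 67% or into no change. These results are plain arithmetic, conditional on a whole grade being used and on the illustrated patterns occurring. How often they would occur is unknown; the range of about 29 to about 1 point in median error, with 25% to 5% of tumours off by more than 50 points, rests on assumed Dirichlet shares.

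The reach is narrow: the exploratory comparison of ER and PR expression between baseline and hysterectomy specimens. The Ki-67 endpoint (Section 10.1), the sample size (Section 11.2) and the primary analysis (Section 11.5) do not use the score. This is a cheap improvement to an exploratory measure and not a threat to the trial's main conclusion.

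**What to change.** In Section 8.1.3, replace the sentence that defines the score with wording such as: *The reader records the percentage of tumour cells at 1+, 2+ and 3+. H score = 1 × (% at 1+) + 2 × (% at 2+) + 3 × (% at 3+), range 0 to 300. The same rule applies to ER and PR in pre- and post-treatment specimens.*

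A smaller alternative is to keep the product and state how the intensity is assigned when staining is mixed. Only an unrounded mean over the stained cells gives the same result as the weighted sum.

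The cost is one sentence and three recorded percentages in place of one intensity and one percentage, on the same slides with the same stain and reader, with slightly longer reading time. Comparability with any earlier series is kept, because a commonest-grade or strongest-grade product can be derived from the three percentages. The reverse is not possible without re-reading the slides, so the change is best made before scoring begins.

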8.1.4 Genomic analyses

Paired tumor/normal whole exome sequencing (WES) and whole transcriptome sequencing (RNAseq) will be performed according to standard protocol methods using Illumina instruments. Endometrial tumor samples before and after protocol treatment will be collected in routine fashion for FFPE collection. Additionally, for normal germline analysis, two 4 mL EDTA blood tubes (purple top) will be collected. We will perform analyses of germline and somatic genomic landscapes, as well as gene expression phenotypes before and after treatment including assessment of driver mutations, mutation signatures, tumor mutation burden, immune signatures.

9.0 STUDY CALENDAR

Protocol Activities All procedures may increase in frequency if clinically indicated.	Screening ^a	Preoperative Window Period	Pre-op ^d	Surgery ^e	Follow-Up Post-surgery
		Day 1			
Informed Consent ^g	X				
Eligibility	X				
Registration	X				
Medical History ^h	X				

Height	X				
Physical Exam	X	X ^c	X		X
Vital Signs ⁱ	X	X ^c	X		X
ECOG Status (Appx. A)	X	X ^c	X		X
Con-med review ^j	X	X ^c	X		X
AE assessment ^k		X	X		X
CBC w/diff, plt	X	X ^c	X		X
Serum chemistry ^l	X	X ^c	X		X
Lipid panel ^m	X	X ^c	X		X
Research blood collection ^p	X				
MA		Twice daily, oral 80 mg			
If receiving combination therapy: PTE		Twice daily, oral 100 mg			
MA drug diary		-----X-----	X		
If receiving combination therapy: PTE drug diary ⁿ		-----X-----	X		
Endometrial biopsy	X ^o			X ^o	
Scheduled total hysterectomy				X	

- a. Screening evaluations to occur within 30 days prior to start of protocol therapy at COH.
- b. Protocol therapy with PTE ± MA is planned for the duration of the preoperative window period. The date of scheduled surgery will define the duration of the preoperative window period and therefore, protocol therapy. In the absence of delay in planned surgery, treatment will last 3 weeks (+/- 7 days). Day 1 is defined as the day of PTE initiation during the preoperative window period. In the case of surgery delay, patients may stop the treatment regimen up to 14 days prior to surgery. If the surgery date is moved up, patients may undergo protocol therapy for less than 3 weeks. **It is not a deviation if the standard of care surgery falls outside the specified window.**
- c. Only perform **if NOT** performed within 7 calendar days prior to D1.
- d. *For participants who end the preoperative window period (i.e. protocol therapy),* pre-op activities to be performed **within 7 days** prior to the scheduled surgery at COH or other institution.
- e. Surgery defined as standard of care total hysterectomy with or without bilateral salpingo-oophorectomy, with or without staging. Surgery may be performed either at COH or at an outside institution.
- f. *Standard of care clinic visits and safety follow-up* to occur post-surgery at **(i) 6 weeks (± 14 days).** **It is not a deviation if the standard of care visit falls outside the specified window.** Follow up visits will take place at a COH clinic site, which includes community clinic sites. Expedited reporting will occur during this period. Safety follow-up may be extended until resolution/stabilization of reportable AEs.
- g. *Informed consent* process to be fully documented (see **Section 16.4**). Informed consent must occur prior to any research only screening procedures.
- h. *Medical history* to include a review of treatment history, any ongoing medical conditions and medical history pertaining to eligibility on study and involvement during study.
- i. *Vital signs:* Weight, heart rate, blood pressure, respiration rate, and temperature.
- j. Concurrent medications and reason for administration to be documented in EHR and reported in the eCRFs from within 28 prior to protocol therapy up to the 6-week post-surgery visit. A medical review of the EHR may be performed if there are any reportable AEs occurring beyond the 6-week post-surgery visit. See **Section 5.9** for concomitant therapy restrictions and guidelines.
- k. Adverse events (AEs) will be assessed using CTCAE v.4.0 and documented from Day 1 of protocol therapy until the 6-week post-surgery visit, at the defined study visits and at standard of care visits. Reportable AEs should be followed until resolution/stabilization of the event.
- l. *Serum chemistry to include:* Albumin, Total Bilirubin, Total Calcium, Bicarbonate, Chloride, Creatinine, Glucose, Alkaline Phosphatase, Potassium, Total Protein, Sodium, ALT, AST, and BUN.
- m. *Lipid panel* to include, Low-density lipoprotein (LDL), triglycerides, total cholesterol, High-density lipoprotein (HDL). May use lipid panel results from up to 6 months prior to treatment start as baseline labs. Laboratory studies may be drawn at laboratories outside of COH.

- n. *Drug diary* for each study agent will be given to the participant and will be reviewed for adherence. See **Appendix C** (PTE) and **Appendix D** (MA). Drug bottles and drug diaries may be collected by the research nurse or investigator, or may be shipped to the study team.
- o. *Endometrial biopsy* at screening time point does not need to be performed if the block is readily available for histologic analysis from a previous endometrial biopsy. The endometrial biopsy at time of hysterectomy is optional.
- p. If not collected at baseline, it may be collected at any time during or after treatment.

